12.1.3. Weight and Height

For measuring weight, a scale with appropriate range and resolution will be used and must be placed on a stable, flat surface. Subjects must remove shoes, bulky layers of clothing, and jackets so that only light clothing remains. They must also remove the contents of their pockets and remain still during measurement of weight.

Height will be measured without shoes.

12.1.4. Physical Examination

Physical examinations will be performed by the Investigator or qualified designee. A complete physical examination will include the oral cavity, head, eyes, ears, nose and throat, cardiovascular system, lungs, abdomen (liver/spleen), extremities, skin, neuropsychiatric mental status and sensory/motor status, musculoskeletal system, and general appearance. A brief physical examination will consist of cardiac and pulmonary auscultation.

The individual performing the physical examination will characterize findings as either normal or abnormal. Clinically significant abnormal physical examination findings found during Screening should be reported on the medical history eCRF. Clinically significant abnormal physical examination findings found after the subject has received study drug will be reported as AEs on the eCRF.

12.1.5. Columbia-Suicide Severity Rating Scale (C-SSRS)

The C-SSRS measures both suicidal ideation and suicidal behavior. When administered, all responses recorded on the scale must be provided by the subject either verbally or by gesture. The Baseline version of the C-SSRS (Section 16.2) will be used during Screening to assess lifetime suicidality. At all other protocol-specified time points, the C-SSRS – Since Last Visit version (Section 16.3) will be used to assess the subject's suicidality since the last assessment. Any changes from baseline assessment should be reported as an AE on the eCRF.

If any item(s) on the C-SSRS are answered with "yes", a physician Investigator must review the subject's responses in order to determine the subject's study eligibility, or continued participation, and potential need for referral to a mental health professional. A significant risk of suicide is defined as a "yes" in answer to: a) questions 4 or 5 on the suicidal ideation section, or b) any questions on any item in the suicidal behavior section. This must be reported as an SAE and followed up accordingly. Additionally, if a subject responds "yes" to any of the suicidal ideation questions 1 to 3, the Investigator should apply clinical judgment to determine the need for reporting as an AE or SAE and the need for any referral.

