6.4. Assessment Tools Used to Achieve Objectives

The assessment tools used to achieve the study objectives are presented in Table 7. Effectiveness and safety endpoints, based on these assessment tools, are defined in Section 7.2.

Objective	Assessment Tools
Primary Objective	
Evaluate the safety and tolerability of LUCEMYRA versus placebo when used during an opioid taper in subjects with chronic non-cancer pain	AE reports, clinical laboratory assessments, monitoring of DILI, vital signs, and C-SSRS
Secondary Objectives	
Estimate the difference between treatment groups in measures related to opioid withdrawal and completion of opioid discontinuation when tapered	Taper completion status, reduction in opioid use, urine drug screen, COWS, MCGI-R, MCGI-S, SOWS-Gossop, SOWS-H
Estimate the difference between treatment groups in measures of effectiveness in pain relief, quality of life, and treatment satisfaction	EQ-5D-5L, HADS, ISI, NRS, SF-36, subject satisfaction, and use of rescue medication for pain

 Table 7:
 Assessment Tools Used to Achieve Objectives

AE = adverse event; COWS = Clinical Opiate Withdrawal Scale; C-SSRS = Columbia-Suicide Severity Rating Scale; DILI = drug-induced liver injury; EQ-5D-5L = EuroQol 5-Dimension 5-Level; HADS = Hospital Anxiety and Depression Scale; ISI = Insomnia Severity Index; MCGI-R = Modified Clinical Global Impression – Rater Version; MCGI-S = Modified Clinical Global Impression – Subject Version; NRS = Numeric Rating Scale; SF-36 = Short Form Health Survey – 36 Items; SOWS-Gossop = Short Opiate Withdrawal Scale of Gossop; SOWS-H = Subjective Opiate Withdrawal Scale of Handelsman

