7.2. Study Endpoints

7.2.1. Safety Endpoints

The following safety endpoints will be assessed:

- Number and percent of subjects reporting treatment-emergent adverse events (TEAEs) by system organ class and preferred term.
- Number and percent of subjects reporting treatment-emergent serious adverse events (SAEs) by system organ class and preferred term.
- Number and percent of subjects reporting TEAEs resulting in study drug discontinuation by system organ class and preferred term.
- Change in vital signs from Baseline to each scheduled evaluation.

- Change in clinical laboratory values from Baseline to each scheduled evaluation.
- Percentage of subjects with treatment-emergent alanine aminotransferase (ALT), aspartate aminotransferase (AST), or alkaline phosphatase >3 × the upper limit of normal (ULN) and total bilirubin >2.0 mg/dL at the same evaluation.
- Percentage of subjects identified as suicide risk with Columbia-Suicide Severity Rating Scale (C-SSRS).

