8.2. Subject Exclusion Criteria

- 1. Has a primary diagnosis of complex regional pain syndrome, central neuropathic pain, somatoform pain syndromes, acute nerve root compression, any acute or progressive infectious, inflammatory, or neurological process.
- 2. Liver disease that requires medication or medical treatment, and/or AST or ALT levels greater than 3 times the ULN.
- 3. Gastrointestinal or renal disease, which would significantly impair absorption, metabolism or excretion of study drug, or would require medication or medical treatment.
- 4. Has a diagnosis of epilepsy or history of seizures.
- 5. Has clinically significant abnormal laboratory value(s).
- 6. Self-reported or evidence of OUD or other substance use disorder within last 12 months prior to Screening using the Sponsor-provided Mini-International Neuropsychiatric Interview.
- 7. Urine toxicology screen positive for any illicit or non-prescribed opioid drugs prior to randomization.
- 8. Taking prescription methadone, buprenorphine, fentanyl rapid acting products, tapentadol, tramadol, butorphanol, meperidine, or levorphanol for any reason.

- 9. Known or suspected pregnancy, planned pregnancy, or lactation.
- 10. Any of the following cardiovascular abnormalities at Screening and before randomization:
 - a. Resting heart rate ≥ 105 bpm or <55 bpm or symptomatic bradycardia;
 - b. Resting systolic blood pressure ≥160 mmHg or <95 mmHg or symptomatic hypotension;
 - c. Resting diastolic blood pressure \geq 90 mmHg or <65 mmHg;
 - d. Clinically significant abnormal electrocardiogram (eg, second- or third-degree heart block, uncontrolled arrhythmia; QT corrected by heart rate by Fridericia's method (QTcF) of ≥450 msec or a history of QT interval prolongation;
 - e. New York Heart Association class III or IV; or
 - f. History of myocardial infarction within 6 months of Screening.

Medications taken for stable hypertension are permitted when dose/regimen has been consistent for a minimum of 3 months prior to screening.

- 11. Any severe or unstable psychiatric disorder including post-traumatic stress disorder, schizophrenia, bipolar disorder, major depression, substance abuse, or suicidality as determined by the Investigator.
- 12. Subject answers "yes" to "suicidal ideation" in prior 24 months to any items 1 through 5 on the C-SSRS, or subject answers "yes" to any lifetime "suicidal behavior" item on the C-SSRS.

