13. STATISTICS

13.1. General Statistical Considerations

This section is an overview of the planned statistical analyses. Additional analyses and details will be provided in the statistical analysis plan, which will be finalized before database lock.

Continuous or ordered categorical variables will be summarized with the mean, standard deviation, minimum, median, and maximum. Categorical variables will be summarized with counts and percentages.

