13.4.2. Safety Analysis

All safety analyses will be performed on the Safety Population using the treatment actually received. All safety summaries will be descriptive; no statistical testing will be performed.

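### Section 12.1.5 gives two conflicting AE rules for new C-SSRS ideation on items 1-3, and the listed suicide-risk endpoint has neither a definition nor a stated method that would capture these responses independently.

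*Combined protocol and SAP*

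**What the plan says.** Section 6.4 (Table 7) names the tools for the primary safety objective: "AE reports, clinical laboratory assessments, monitoring of DILI, vital signs, and C-SSRS". Tables 2 and 3 schedule the C-SSRS at Screening and at every clinic visit.

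Section 12.1.5 contains three reporting statements:

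- A general rule: "Any changes from baseline assessment should be reported as an AE on the eCRF".
- A rule for significant risk of suicide, defined as a 'yes' to "questions 4 or 5 on the suicidal ideation section, or b) any questions on any item in the suicidal behavior section". These responses must be reported as an SAE.
- A rule for a 'yes' to ideation items 1-3: "the Investigator should apply clinical judgment to determine the need for reporting as an AE or SAE and the need for any referral".

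Exclusion 12 in Section 8.2 removes a candidate if "Subject answers 'yes' to 'suicidal ideation' in prior 24 months to any items 1 through 5 on the C-SSRS", or if any lifetime suicidal behavior is endorsed.

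Section 7.2.1 and the synopsis list a C-SSRS safety endpoint, the percentage of subjects identified as suicide risk. Section 13.4.2 says "All safety summaries will be descriptive; no statistical testing will be performed". Its subsections cover adverse events, laboratory tests, ECG and vital signs. Section 13.1 adds that "Additional analyses and details will be provided in the statistical analysis plan, which will be finalized before database lock".

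**The concern.** The general rule and the item 1-3 rule give different instructions for the same response. The general rule has no exception, and the item 1-3 rule does not say that it overrides the general one. The synopsis lists 7 centers. One center could record every new 'yes' to items 1-3 as an AE while another records only those its Investigator thinks need reporting, and both could point to the text.

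This matters for the analysis because the stated results may have no other route for these responses. The AE tables depend on what sites choose to enter, and the one C-SSRS endpoint may not count items 1-3. The by-arm count of new, milder ideation would then reflect reporting practice rather than the scale responses, which are collected in a standard way from every subject.

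**Working it through.** No figure in the plan is in dispute, so the main check sets the passages side by side.

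**1. Which responses fall under both rules?** The general rule applies to any change from the baseline assessment. The item 1-3 rule applies to any 'yes' on those items. Exclusion 12 means that an enrolled subject has no ideation on items 1-5 in the 24 months before Screening. A post-dose 'yes' to items 1-3 is therefore a change from the recent baseline and meets both rules. There are two limits:

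- Section 12.1.5 says the Baseline version assesses lifetime suicidality. A subject whose ideation is older than 24 months is eligible with a lifetime 'yes', and a later 'yes' from that subject is not clearly a change from baseline.
- Section 12.2.3 starts AE collection with dosing on Day 1, so a pre-dose response at Visit 1 is outside AE reporting.

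**2. Do the rules conflict for the other items?** No. Items 4-5 and any behavior must be reported as an SAE, which is compatible with the general rule. The conflict is confined to items 1-3.

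**3. Does the listed endpoint capture items 1-3?** Section 7.2.1 uses the phrase 'identified as suicide risk' without defining it. The only definition on offer is that of significant risk in Section 12.1.5, which requires items 4-5 or behavior. If that definition is used, items 1-3 are outside the endpoint. No section says that it is to be used.

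**4. Does Section 13.4.2 supply a method?** Section 7.2.1 has seven safety endpoints. TEAEs, serious TEAEs, TEAEs leading to discontinuation, laboratory change, the liver criterion and vital signs all reappear in Section 13.4.2. C-SSRS is the only one that does not.

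**5. How much could reporting practice matter?** Section 7.3 plans 30 subjects per arm, so one subject is 1/30 = 3.3%. The documents give no incidence of new item 1-3 ideation. The values of p below, and the assumption that half of cases are reported, are illustrative only. The expected count per arm is 30p. The chance of at least one case in an arm is 1 − (1 − p)^30. If half are reported as AEs, the chance that at least one reaches the AE tables is 1 − (1 − p/2)^30.

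| Assumed p | Expected per arm | At least one case | At least one reported (half reported) |
|---|---|---|---|
| 2% | 0.6 | 1 − 0.98^30 = 46% | 1 − 0.99^30 = 26% |
| 5% | 1.5 | 1 − 0.95^30 = 79% | 1 − 0.975^30 = 53% |
| 10% | 3.0 | 1 − 0.90^30 = 96% | 1 − 0.95^30 = 79% |

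With expected counts between 0.6 and 3, the reporting decision can determine whether an arm shows any case.

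**The case against.** The strongest reply has five parts.

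- **A C-SSRS analysis is listed.** A reader might infer from the silence of Section 13.4.2 that none is planned. The documents do not support that: Section 7.2.1 and the synopsis list a percentage endpoint, and Section 13.4.2 says that safety summaries are descriptive. Section 13.1 also defers detail to a SAP. This part stands. What is missing is a definition and a stated method.
- **The endpoint is not shown to exclude items 1-3.** Nothing ties its wording to the significant-risk definition. This also stands, and the consequence is conditional on that definition being used.
- **The rules might be compatible.** The judgment could be read as choosing only between AE and SAE. The sentence does not say so, however; judging the need for reporting naturally includes deciding whether to report at all.
- **Other safeguards exist.** Any 'yes' must be reviewed by a physician Investigator, and Section 13.5 puts suicidality within the DMC charter. These reduce the practical risk to subjects, but neither is a reported result.
- **The yield may be low.** This is a descriptive pilot with 21 to 27 days of study drug, in a population screened for recent ideation, and the gravest responses have a clear SAE rule. That is fair, and it is why the assumed incidences carry no weight as predictions.

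**Conclusion.** The contradiction in Section 12.1.5 is real, is confined to ideation items 1-3, and applies to nearly all such post-dose responses. A reader might infer that it applies to every one; lifetime ideation older than 24 months prevents that conclusion.

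A reader might also infer that items 1-3 can reach the results only through AE reports. The documents support this only on two conditions: that the endpoint takes the significant-risk definition of Section 12.1.5, and that the separate SAP, which was not supplied, adds no C-SSRS summary. If both hold, the reported by-arm frequency of new item 1-3 ideation would depend on which sentence a site follows.

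The size cannot be estimated from the documents. What is certain is the granularity: each case reported or left out moves an arm by 3.3 percentage points. Because this bears on a named tool for the primary objective and costs little to correct, the sponsor should correct it.

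**What to change.** 1. In Section 12.1.5, reconcile the general rule with the item 1-3 rule so that one instruction applies. This review takes no position on which reporting rule is right.
2. In Section 7.2.1 and the synopsis, define 'identified as suicide risk' by C-SSRS item.
3. In Section 13.4.2, add a descriptive table by arm in the Safety Population: number and percent of subjects with any post-dose 'yes' to ideation items 1-3, to items 4-5, and to any behavior item. Take it from the scale itself, so that it does not depend on the AE decision. State how a pre-dose response at Visit 1 and lifetime ideation older than 24 months are handled.

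The cost is a wording change in Section 12.1.5, one definition, and one extra table from data already collected. No new assessment or visit is needed.

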12.1.6. Electrocardiogram

Standard 12-lead electrocardiograms will be performed. Electrocardiograms should be performed before blood draws and after the subject has rested quietly for at least 10 minutes in a supine position. The Investigator (or Investigator's designee who is a physician) will interpret the electrocardiogram and will record his/her global interpretation of the electrocardiogram (ie, normal or abnormal) on the tracing. Each electrocardiogram tracing must also include the signature of the Investigator and the date that the electrocardiogram was interpreted. If the global interpretation is abnormal, the Investigator will indicate on the tracing whether the abnormality is clinically significant or not clinically significant. Clinically significant electrocardiograms should be repeated up to 2 times after another rest of at least 10 minutes. A copy of each electrocardiogram and the physician's assessment will be filed with the source documents.

During the study, when any QTcF interval is \geq 495 msec, 2 additional electrocardiograms should be taken at 10- to 15-minute intervals (electrocardiograms should be done after the subject has been resting for at least 10 min). The QTcF interval on all electrocardiograms should be confirmed by the Investigator. If it is determined that 2 of the 3 QTcF intervals exceed 500 msec or >25% above screening value, then the subject will be discontinued from the study.

12.1.7. Laboratory Assessments

See Table 10 for the list of clinical laboratory tests to be performed. Additional tests may be performed at any time during the study as determined necessary by the Investigator or required by local regulations. All study-required laboratory assessments will be performed by a central laboratory.

The Investigator must review the laboratory report and document this review. The laboratory reports must be filed with the source documents. Clinically relevant changes during the study that result in changes in study drug, study participation, or concomitant treatment use will be recorded as AEs on the eCRF. Clinically significant abnormal laboratory findings are those which are not associated with the underlying disease, unless judged by the Investigator to be more severe than expected for the subject's condition.

All laboratory tests with values considered clinically significantly abnormal during participation in the study should be repeated until the values return to normal or baseline or are no longer considered clinically significant by the Investigator or medical monitor. If such values do not return to normal/baseline within a period of time judged reasonable by the Investigator, the etiology should be identified, and the Sponsor notified.

All testing for opioids in the urine is qualitative, including confirmatory testing. Qualitative results will be reported for opioids by class with dipstick tests and by opioid analyte for urine specimens sent to the Sponsor's central laboratory. No quantitative testing for opioids will be performed or reported throughout the study.

All protocol-required laboratory assessments must be conducted in accordance with the laboratory manual.

Hematology ^a	Chemistry ^b	Urinalysis
Hemoglobin	Cholesterol	Color
Hematocrit	Triglycerides	Clarity
Red blood cells	Sodium	pН
Mean corpuscular volume	Potassium	Specific gravity
Mean corpuscular hemoglobin	Chloride	Protein
Mean corpuscular hemoglobin concentration	Carbon dioxide	Glucose
Red blood cell distribution width	Glucose	Ketones
White blood cell count	Creatinine	Bilirubin
Neutrophils	Albumin	Nitrite
Lymphocytes	Total protein	Blood
Monocytes	Calcium	Urobilinogen
Eosinophils	Phosphorus	White blood cell count
Basophils	Aspartate aminotransferase	Red blood cell count
Platelet count	Alanine aminotransferase	Epithelial cells
Prothrombin time	Gamma-glutamyl transpeptidase	Bacteria
Activated partial thromboplastin time	Total bilirubin	Casts
	Lactate dehydrogenase	Crystals
	Alkaline phosphatase	Leukocyte esterase
	Blood urea nitrogen	
	Thyroid-stimulating hormone	
	Free thyroxine	

Table 10: Clinical Laboratory Tests

^a Blood will be collected in anticoagulant containing evacuated venous blood collection tubes (eg, VacutainerTM).

^b Blood will be collected in serum separation evacuated venous blood collection tubes (eg, Vacutainer[™]) and serum separated according to standard procedures.

Urine testing will be done for ethyl glucuronide, a metabolite of ethanol that is stable in urine and detectable up to 3 days after ingestion of alcohol. The first positive test for alcohol during the study should prompt subject counseling about the important in abstaining from alcohol use during the study. More than 2 positive tests for alcohol after Screening will require discontinuation from the study.

Qualitative urine drug screening for illicit use will be performed at Screening for all subjects and at every clinic visit for the following drugs: amphetamines/methamphetamines, cocaine, barbiturates, opiates, benzodiazepines, cannabinoids, methadone, and buprenorphine. The central lab will provide standard sets of urine drug screen "dipsticks" for use across all sites. Quantitative confirmatory testing for illicit substances may be performed when results contradict subject self-report. Confirmed evidence of use of illicit substances will require discontinuation from the study.

A urine pregnancy test designed to measure human chorionic gonadotropin will be performed for all female subjects, regardless of childbearing potential.

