AE = adverse event; COWS = Clinical Opiate Withdrawal Scale; C-SSRS = Columbia-Suicide Severity Rating Scale; EOS = end of study; EQ-5D-5L = EuroQol 5-Dimension 5-Level; HADS = Hospital Anxiety and Depression Scale; HIPAA = Heath Insurance Portability and Accountability Act; ISI = Insomnia Severity Index; MCGI-R = Modified Clinical Global Impression – Rater Version; MCGI-S = Modified Clinical Global Impression – Subject Version; MED = morphine equivalent dose; MINI = Mini-International Neuropsychiatric Interview; PC = phone call; PE = physical examination; RC = reminder contact; SF-36 = Short Form Health Survey – 36 items; SOWS-Gossop = Short Opiate Withdrawal Scale of Gossop; SOWS-H = Subjective Opiate Withdrawal Scale of Handelsman

^a The Screening Visit may be conducted over the course of multiple visits, as needed.

^b Subjects who experience intolerable withdrawal symptoms may temporarily suspend the opioid taper once (Section 9.3). See study drug taper schedule in Section 9.2.3.

^c Phone call 30 days after the last dose of study drug. See Table 4 for other assessments to be captured during the phone call, in addition to follow-up on any outstanding AEs or concomitant treatment usage.

^d The subject's baseline opioid use and changes to doses for planned taper reductions should be submitted to and approved by the Medical Monitor prior to Day -1.

^e All female subjects, regardless of childbearing potential.

^f Confirmatory quantitative testing for illicit substances identified in qualitative testing results may be performed.

^g Subjects should refrain from alcohol consumption during the study. Repeated alcohol use (eg, 2 positive tests for alcohol after Screening) during the study requires subject discontinuation.

^h On Day 1, orthostatic vital signs should be assessed pre-dose and 1-hour post-dose of study drug. A post-dose assessment is not required after Day 1 at clinic visits. During phone calls, at-home vital signs (systolic and diastolic blood pressure and pulse) should be recorded after the subject rest for at least 5 minutes.

ⁱ Baseline version at Screening and 'Since Last Visit' version at subsequent visits.

^j Phone calls will include review of an at-home vital signs assessment by the subject, an assessment of how the subject is feeling, and review of any changes to study drug dosing.

- ^k Phone call will take place on Day 19, to check on the subject's well-being and to assess how the subject is feeling.

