8.5. Subject Discontinuation Criteria

The Investigator or Sponsor may discontinue individual subjects from the study at any time if it is deemed clinically appropriate or for any reason, including the following:

- Cardiovascular events
 - QTcF >500 msec or >25% above screening value for both males and females.
 - New onset of clinically significant abnormal electrocardiogram (eg, second- or third-degree heart block or uncontrolled arrhythmia, prolonged QTcF interval).
 - Persistent signs or symptoms of hypotension, bradycardia, or hypoperfusion.

- Single occurrence of symptomatic bradycardia (as assessed by the Investigator, regardless of blood pressure) associated with chest pain, shortness of breath, or decreased level of consciousness.
- Medical intervention for cardiovascular event: Any medical intervention (nonmedication or medication inclusive) used for the treatment of any cardiovascular event, with the exception of a positional intervention in subjects displaying hypotension.
- Any other clinically significant cardiovascular signs or symptoms that would place the subject at risk.
- Evidence of repeated alcohol use (eg, 2 positive alcohol tests after Screening) during the study. Alcohol or other sedative/hypnotic withdrawal signs and symptoms developing following enrollment into the study.
- More than 2 repeat occurrences of opioid rescue medication usage reported by the subject after Screening.
- An intolerable AE or SAE; the relationship to study drug must be recorded in source.
- Requirement for a treatment that is prohibited (Section 9.4) by the protocol.
- Noncompliance with the protocol, including but not limited to showing evidence of illicit drug use while participating in the study or refusal or inability to continue opioid taper schedule per protocol.
- Lost to follow up: If a subject is lost to follow-up, repeated attempts (defined as a minimum of 3 telephone calls, followed by sending a letter) will be made to reach the subject. If repeated attempts are unsuccessful, lost to follow up will be recorded in the subject's source document and electronic case report form (eCRF) as the reason for early discontinuation.

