8.6. Early Discontinuation Visit

If a subject is discontinued from the study before completion, regardless of whether they have received study drug, the reason for discontinuation must be documented in the subject's source document and eCRF. Whenever a subject is discontinued, the procedures/assessments listed for the EOS Visit in the Schedule of Assessments (Table 2 or Table 3) should be performed. If a subject discontinues on a scheduled visit, assessments completed at that visit should be entered into the eCRF for that scheduled visit. Assessments required for the EOS Visit that are not required at the scheduled visit (eg, a complete physical examination, clinical laboratory tests) should be completed and entered into the eCRF for the EOS Visit.

Subjects who prematurely discontinue the study will be instructed to taper study drug as described in Section 9.2.3 and to complete the at-home assessments for the study drug taper period (Table 4 or Table 5). Once discontinued, subjects may not re-enter the study.

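### At exactly two positive post-Screening alcohol tests, footnote g of Tables 2 and 3 requires discontinuation, section 8.5 permits it and section 12.1.7 does not require it (secondary: the repeat-ECG trigger in 12.1.6 omits the 25% QTcF criterion)

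*Combined protocol and SAP*

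**What the plan says.** **Alcohol.** Three places set the consequence of repeated positive tests.

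- Section 12.1.7: "The first positive test for alcohol during the study should prompt subject counseling", and then "More than 2 positive tests for alcohol after Screening will require discontinuation from the study". It gives no instruction for the second positive.
- Section 3.3, footnote g of Table 2, repeated word for word in Table 3: "Repeated alcohol use (eg, 2 positive tests for alcohol after Screening) during the study requires subject discontinuation".
- Section 8.5 lists "Evidence of repeated alcohol use (eg, 2 positive alcohol tests after Screening) during the study" as a ground for discontinuation, under the lead-in "The Investigator or Sponsor may discontinue individual subjects from the study at any time if it is deemed clinically appropriate".

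The alcohol test detects ethyl glucuronide, described in 12.1.7 as "a metabolite of ethanol that is stable in urine and detectable up to 3 days after ingestion of alcohol".

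**QTcF.** Section 12.1.6 asks for two further tracings when a QTcF is 495 msec or more. The subject is discontinued if two of the three values are over 500 msec or more than 25% above screening. It also has clinically significant ECGs repeated up to twice. Section 8.5 lists the same two QTcF limits as discontinuation grounds, without the two-of-three step.

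**The concern.** The alcohol rule is a mandatory stopping rule whose threshold depends on which page the site reads. A site working from the schedule of assessments removes the subject at the second positive. A site working from 12.1.7 counsels at the first and has no instruction to remove anyone until the third. The second site departs from footnote g while following the body text.

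Three things are at stake: avoidable protocol deviations, uneven handling across the 7 centers, and noise in endpoints that depend on retention (time to study drug discontinuation and possibly taper completion). Alcohol also bears on the primary safety objective. Section 12.1.7.1 names binge drinking as an alternative explanation for liver injury, 9.4.2 allows acetaminophen up to 4 g per day, and the Data Monitoring Committee charter is to address alcohol results (13.5).

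For QTcF, a reading can exceed the 25% limit without setting off the numeric trigger for the tracings that would confirm it.

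**Working it through.** **1. The rules side by side**

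| Post-Screening positives | Footnote g | 8.5 | 12.1.7 |
|---|---|---|---|
| 1 | no action stated | no action stated | counsel |
| 2 | must discontinue | may discontinue | no action stated |
| 3 or more | must discontinue | may discontinue | must discontinue |

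The texts conflict only in the row for exactly two. Discontinuing there satisfies every sentence; retaining the subject satisfies 12.1.7 and 8.5 but not footnote g.

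**2. Can it arise?** Alcohol tests after Screening fall on Days 1, 3, 8, 15, 22 and 28 (6 tests, Table 2) or Days 1, 3, 8, 15, 21, 28 and 34 (7 tests, Table 3). Either threshold can be reached.

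**3. Could one drinking episode give two positives?** Day 1 has no visit window and Visit 2 is Day 3 ± 1, so the samples are 1, 2 or 3 days apart. With detection up to 3 days, alcohol taken up to 3 − 1 = 2, 3 − 2 = 1 or 3 − 3 = 0 days before the Day 1 sample could be positive at both. The protocol does not say whether that pair counts as repeated use.

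**4. When could it affect the opioid taper?** Let t be the days from sampling to action. Section 12.1.7 says "All study-required laboratory assessments will be performed by a central laboratory", but gives no turnaround, so t is unknown. To act before the step to zero opioid:

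- Standard schedule, step on Day 13, action by Day 12: a second positive on Day 3 needs t ≤ 9; on Day 8, t ≤ 4.
- Pause schedule, step on Day 19, action by Day 18: Day 3 needs t ≤ 15; Day 8, t ≤ 10; Day 15, t ≤ 3.

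**5. Effect on study drug exposure.** Section 8.6 states: "Subjects who prematurely discontinue the study will be instructed to taper study drug as described in Section 9.2.3". Every regimen in 9.2.3 takes 4 days (1+2+1, 2+2, 2+2, 4). For a positive on day d, the last dose is about d + 4 + t. At t = 0:

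| Schedule | Second positive | Last dose | Planned | Days earlier |
|---|---|---|---|---|
| Standard | Day 3 | 7 | 21 | 14 |
| Standard | Day 8 | 12 | 21 | 9 |
| Standard | Day 15 | 19 | 21 | 2 |
| Pause | Day 15 | 19 | 27 | 8 |
| Pause | Day 21 | 25 | 27 | 2 |

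Each day of turnaround takes one day off the difference.

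**6. Size for one subject.** The plan's own figures first. Section 13.2 gives half-widths of 0.24 (n = 20 per group) and 0.17 (n = 40) for a difference of 0.2. Rates are not stated, but 0.1 and 0.3 reproduce them: 1.96 × √((0.09 + 0.21)/20) = 0.240 and 1.96 × √(0.30/40) = 0.170. At n = 30 the result is 1.96 × √(0.30/30) = 0.196. That figure is for adverse withdrawal events. For taper completion, 13.4.1.1 adds a continuity correction of (1/30 + 1/30)/2 = 0.033, giving 0.229, about 0.23. With completion near 50% in both arms (an assumption), it is 1.96 × √(0.50/30) + 0.033 = 0.286, about 0.29. One subject moves an arm's proportion by 1/30 = 3.3 percentage points.

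**7. QTcF.** The 25% limit is 1.25 × screening. It lies below the 495 msec trigger when screening is below 495/1.25 = 396 msec. Example: screening 380, reading 480, a rise of 480/380 − 1 = 26.3%, below 495. From 396 msec up to the entry ceiling (450 and above is excluded), the limit is 495 to under 562.5, so there is no gap. The share of subjects below 396 msec is not given.

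**The case against.** **The count in footnote g is only an example.** The operative term is repeated use, so a site that judges two positives to be one episode might keep the subject under both texts. This does not remove the conflict, because the footnote names two positives as an instance of what requires removal. It does stand for the Day 1 and Day 3 pair, which may be a single episode, and that is why a clarifying sentence is needed whichever number is chosen.

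**More than 2 may be the intended threshold.** It matches the opioid-rescue rule in 8.5 and 9.4.2. This stands as a reason not to presume the sponsor's intent. It also shows that 8.5 distinguishes 2 from more than 2, so the two are not loose synonyms.

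**A compliant path exists.** Discontinuing at two breaches nothing. True, but the sequence in 12.1.7 leads a site away from it.

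**QTcF is already handled.** Clinically significant ECGs are repeated, 8.5 names a prolonged QTcF interval as an example of one, and ECG-laboratory measurements go to the Investigator (13.4.2.1.3). The eligibility criteria list 450 msec or more among such abnormalities; applied during the study, that standard would leave a gap only for screening values below 450/1.25 = 360 msec. This largely stands. What remains is reliance on judgement where a number is available.

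**Stronger readings to avoid.** A reader might infer that the alcohol conflict biases the comparison between arms. Nothing in the documents supports that: the same text applies to both arms under blinding. Nor is the QTcF gap a contradiction, since no sentence in 12.1.6 conflicts with 8.5.

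**Conclusion.** The alcohol threshold is wrong as written: one count carries three different instructions and no section sets an order of precedence. The textual finding is firm; its consequence is minor. The number of subjects with exactly two positives cannot be derived from the documents.

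A second positive by Day 8 (standard schedule) or by Day 15 (pause schedule) could lead to removal before the final opioid step, if the result is acted on in time. That this changes taper completion is an assumption, because 13.4.1.1 refers to components of successful completion without listing them. If it does, one subject shifts an arm by 3.3 points, small against a half-width of about 0.23 at assumed rates of 0.1 and 0.3. The reason to act is consistent handling and avoidable deviations rather than a material effect on the estimates.

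The QTcF point is secondary: a cheap safety improvement limited to screening values below 396 msec, already partly covered by clinical judgement.

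**What to change.** **Alcohol.** Use one threshold throughout. The smallest edit replaces *More than 2* with *2 or more* in 12.1.7. That matches footnote g in count and force, and 8.5 in count only; 8.5 still says *may*, as it does for its whole list. On the reading that footnote g already covers two positives, no further subjects are lost. If the sponsor intends 3, change footnote g in both tables and 8.5 instead, and leave 12.1.7. Either way, add a sentence saying whether Day 1 and Day 3 positives that fall within the 3-day detection window count as one episode.

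**QTcF.** Extend the 12.1.6 trigger to: *495 msec or more, or >25% above screening value*. Leave the QTcF criterion in 8.5 as it is.

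**Cost.** A few sentences in one protocol amendment, with IRB/IEC submission. The alcohol change needs no new data. The QTcF change adds two repeat ECGs for each reading in the gap.
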